4.1 Potential Risks

Risks include withdrawal symptoms and side effects from the medications, described below.

Nicotine Withdrawal Syndrome

Most individuals who quit smoking experience symptoms of withdrawal. These symptoms can occur almost right away and last for 10-14 days. These symptoms include:

- Sadness and mood changes
- Insomnia or changes in sleep
- Constipation
- Decreased heart rate
- Irritability
- Craving for cigarettes
- Anger
- Difficulty concentrating
- Restlessness or nervousness
- Appetite increase and weight gain

Nicotine Patch

The potential side effects of the nicotine patch are described below:

Most Common Side Effects. Nausea, vomiting, dizziness, weakness, and rapid heartbeat are side effects that occur rarely, but are most often caused by continuing to smoke while using the patch. Difficulty breathing or a notable rash could be the symptoms of an allergic reaction.

Skin Reactions. The most common skin reactions to the patch are skin redness, rash or swelling, itching, bumping or tingling at the patch site. To minimize these reactions, the site of the patch can be changed each day.

Sleep Disturbances. When using the patch, some people also report difficulties sleeping or vivid dreams. However, this is rare and can be minimized by removing the patch at night.

Other Nicotine Patch Risks. These include risks to children and pets if the nicotine patches are not stored or disposed of properly. Unused and used patches have enough nicotine to poison children and pets.

Varenicline (Chantix®)

The potential side effects of taking varenicline are described below:

Most Common Side Effects. Potential side effects of taking varenicline are nausea, sleep disturbance, constipation, flatulence (gas), or vomiting. These can occur in more than 5% of people taking this medication.

Allergic Reactions. There have been rare reports of allergic and skin reactions to varenicline, including swelling of the face, mouth (tongue, lips, and gums), extremities, and neck (throat and larynx). These types of allergic reactions are considered serious and may be life-threatening. However, the risk for these reactions is small (about 1 out of 1000 people taking this medication).

Mood-related Side Effects. Rare serious mood-related effects have been reported in a small number of persons taking varenicline. The risk for this type of reaction is about 1 out of 1000 people taking the medication. These include, but are not limited to, depression, agitation, hostility, suicidal thoughts, suicide attempts, and completed suicide. Some reported cases may have been complicated by the symptoms of nicotine withdrawal in patients who stopped smoking. Depressed mood may be a symptom of nicotine withdrawal. Depression, rarely including suicidal thoughts, has been reported in smokers undergoing a smoking cessation attempt without medication. However, some of these symptoms have occurred in patients taking varenicline who continued to smoke. When symptoms were reported, most occurred during treatment with varenicline, while some followed discontinuation of varenicline therapy. All patients being treated with varenicline will be assessed for such symptoms. These events have occurred rarely in patients with and without pre-existing psychiatric disease.

Although patients with serious psychiatric illness such as major depressive disorder, schizophrenia, or bipolar disorder did not participate in the pre-marketing studies of varenicline, recent clinical trials that specifically targeted these patient populations have demonstrated safety of varenicline for use in these populations. These studies did not find significant differences in mood-related side effect rates or any exacerbation of psychiatric symptoms between those taking varenicline versus placebo.

Cardiac Side Effects. Varenicline may be associated with an increased risk for certain cardiac (heart) and vascular (blood vessel) side effects, including chest pain, heart attack, stroke, shortness of breath, calf pain when walking or sudden onset of weakness, numbness or difficulty speaking. One study showed that these risks are rare (~1% or 1 out of 100 people using varenicline) but a later study found no difference between placebo and varenicline in terms of these cardiac risks.

Somnambulism. Cases of somnambulism (sleep walking) have been reported in patients taking varenicline.

Brief Cognitive Side Effects. Varenicline may cause noticeable drowsiness, dizziness, headache, loss of consciousness, or difficulty concentrating that may impair one's ability to perform tasks requiring judgment or motor and cognitive skills such as driving a car and operating machinery.

Risk of Seizure. Varenicline may be associated with new or worsening seizures during the first month of treatment. Some patients who reported experiencing a seizure while taking varenicline had no prior history of seizures, whereas others had a history of seizure disorder that was remote or well-controlled.

Potential Interaction with Alcohol. It is possible that varenicline may affect response to alcohol. Some individuals have reported lower alcohol tolerance, aggressive behavior, or impaired memory following consumption of alcohol during varenicline treatment. In these cases, the amount of alcohol consumed was not sufficient to explain the event. It is best to minimize or reduce alcohol intake (no more than 3 drinks per occasion or within a 24-hour time period).

Other Risks

Assessments/Questionnaires and Smoking Cessation Counseling. Some people can experience anxiety and other types of general distress when they complete questionnaires. This is generally related learning about some of the health risks associated with smoking. These reactions are usually very mild and typically diminish with time.

Threats to Privacy/Confidentiality. Every attempt will be made by the investigators to maintain all information collected in this study strictly confidential. However, social harms may result when sensitive and personal information is inappropriately disclosed. Inappropriate disclosure of study data about participants' beliefs, attitudes, behavior (including smoking), and health may result in damage to participants' economic status. These harms can include loss of employment, health insurance, life insurance, housing, and ability to travel.

Reproductive Risks [Females Only]. Because of the effects of varenicline and the nicotine patch, there could be serious harm to unborn children or children who are breast-feeding. These effects could also harm the mother. It is also possible that harmful side effects that are not yet known could happen to both the mother and unborn or breast-feeding child.

4.2 Protections Against Risks

The risks associated with the use of study medications will be explained to all participants. This information will also be included in the informed consent forms. We will include a specific measure of side effects associated with study medications that will be administered at two time points during the course of the study. Information will also be provided to participants on how to contact study personnel and other clinical care should a concern arise between assessment time-points. In the event of significant medication side effects, or for any reason, patients can discontinue medication at any point during the study. Accepting medication is not a condition for participation, nor is participating in the study necessary to receive smoking cessation services. Furthermore, during the enrollment phase of the study, when medications will first be initiated, patients will be under the care of an attending physician and will continue to have access to care for the duration of the study.

To protect against the threats to privacy/confidentiality, safeguards will be put into place to minimize the risk of unauthorized access to records (see section 6.0). To minimize the reproductive risks, female participants 55 and under will be screened for pregnancy and advised to use birth control. Pregnant women or women who intend to become pregnant will be excluded from participation. Women will also be advised to inform study personnel in the event they become pregnant.

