3.3 Study Procedures & Data Collection

The following study procedures will be implemented. A description of the measures used to collect data during these procedures is provided below.

- **Intake Session (completed during clinic visit)**
 - Participants will complete a self-report survey of demographics, smoking history, and beliefs about the use of smoking cessation aids.
 - **[Women only]** A pregnancy screen will be administered for women capable of becoming pregnant (55 and under). NOTE: For safety reasons, pregnant women will not be eligible to participate in the research study.
 - The research assistant will complete the blood draw to be used for a nicotine metabolite ratio (NMR) test and arrange for the sample to be transported to the laboratory for processing.
- **Randomization:** Following completion of the 'intake session' and receipt of NMR testing results, participants will be randomized in a 1:1 ratio to either of the following conditions:
 - **Treatment Plan Option 1 (Standard Care):** Standard smoking cessation counseling will be offered + participant choice of nicotine patches or varenicline. Participants are also free to decline either medication.
 - **Treatment Plan Option 2 (Precision Pharmacotherapy):** Standard smoking cessation counseling will be offered + a recommendation to take either the nicotine patch or varenicline based on the results of the NMR test. Regardless of the recommendation, it would still remain the participant's choice to be prescribed either nicotine patches or varenicline. Participants are also free to decline either medication.
- **Pre-Quit Telephonic Visit:** This visit will take place after the NMR results have been received and randomization is complete, approximately 7-14 days following the intake session (depending on lab processing time).

- Participants will be informed of their treatment condition, including the recommended medication if assigned to 'treatment plan option 2' (i.e., the precision pharmacotherapy arm).
- Participants will be offered their choice of either the nicotine patch or varenicline. Participants will be reminded that taking medication is not a condition of participation in the study. In addition, participants assigned to 'treatment plan option 2' (i.e., the precision pharmacotherapy arm) will not be required to accept only the medication recommended to them based on the results of NMR testing.

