- For participants who elect to take a medication, the research assistant will communicate with the study physician ([name]), or the investigators at the Center for Advanced GYN & Minimally Invasive ([name] or [name]) to arrange for a prescription and/or referral to the Delaware Quitline, per participant preference.
- Even for participants who receive a prescription in the clinic or at the Center for Advanced GYN & Minimally Invasive Surgery, a referral to speak with a smoking cessation counselor, which is made available at no-cost to all Delaware residents through the Delaware Quitline.
- Follow-up Telephonic Visit:** This session will occur one week after the pre-quit telephonic/virtual visit.
 - Participants will answer brief questions regarding medication use, quit date or smoking rate if still smoking, and side effects.
- In-Person Assessment:** This session will occur four weeks after the pre-quit telephonic/virtual visit. The research assistant will arrange to meet participants at the clinic.
 - Participants will again complete a brief assessment of medication use, quit date or smoking rate if still smoking, and side effects.
 - Participants who self-report smoking cessation will complete a carbon monoxide (CO) reading by breathing into a machine provide a biochemical confirmation of smoking status.

The measures referenced above will be administered accordingly:

Study Measure	Intake Session Enrollment (in-person)	Pre-Quit Visit Week 0 (phone)	Follow-Up Visit Week 1 (phone)	Final Assessment Week 4 (in-person)
Demographics	X			
Smoking History	X			
NMR	X			
Medication use, quit date or smoking rate, side-effects			X	X
Carbon Monoxide reading				X

- **Demographics.** The research assistant will confirm demographic data collected from the EHR and collect additional characteristics, including address, phone number, date of birth, race/ethnicity, employment status, education level, and income.
- **Smoking history.** Participants will be asked standard questions about cigarette use, including the number of cigarettes smoked per day, the age of smoking onset, whether the participant ever quit smoking previously and for how long, and whether the participant ever utilized smoking cessation aids previously. In addition, participants will be administered the first item from the Fagerström Test for Nicotine Dependence (FTND), a measure of nicotine tolerance and withdrawal.¹⁷

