- **Nicotine Metabolite Ratio (NMR).** NMR testing for cotinine and 3-hydroxycotinine following standard procedures at a commercial laboratory contracted with ChristianaCare (i.e., Quest).¹⁹
- **Medication use quit date or smoking rate, and side effects.** At the follow-up call and in-person assessment, the research assistant will use the timeline follow-back interview method²⁰ to ask participants whether they quit smoking (including the quit date). If participants did not successfully quit smoking, current rates of smoking will be assessed. In addition, the research assistant will ask about medication usage and side-effects.
- **Carbon monoxide reading.** For participants self-reporting smoking cessation, biochemical verification of smoking status will be conducted with the use of a breath carbon monoxide monitor manufactured by Vitalograph according to standard procedures.²¹

4.0 RISKS AND BENEFITS TO PARTICIPANTS:

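### The side-effect checklist is first given after medication is offered, so symptoms already present at entry can be recorded as side effects and worsening from entry cannot be seen

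*Protocol*

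**What the plan says.** Protocol section 4.2 promises a dedicated instrument: "We will include a specific measure of side effects associated with study medications that will be administered at two time points". Section 3.3 fixes the timing. In its measures table, the row "Medication use, quit date or smoking rate, side-effects" is marked at Week 1 (phone) and Week 4 (in person) and is blank at intake and at the Week 0 pre-quit call. The visit descriptions agree. At Week 1, "Participants will answer brief questions regarding medication use, quit date or smoking rate if still smoking, and side effects". At Week 4, "Participants will again complete a brief assessment of medication use, quit date or smoking rate if still smoking, and side effects".

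The contacts before treatment collect other things. At intake, "Participants will complete a self-report survey of demographics, smoking history, and beliefs about the use of smoking cessation aids"; a pregnancy screen and the blood draw for the nicotine metabolite ratio (NMR) complete that visit. The pre-quit call tells participants their arm and offers medication.

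On mood, section 4.1 undertakes that "All patients being treated with varenicline will be assessed for such symptoms", and it also warns: "Depressed mood may be a symptom of nicotine withdrawal". Section 5.0 has staff use a side-effects checklist to establish what has to be reported. It states that there will be no Data Safety Monitoring Board and that monitoring rests with the principal investigator and research team. The SAP contains no side-effect analysis.

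**The concern.** A symptom checklist first given after treatment is offered shows what a participant has now. It does not show whether the symptom is new. Section 4.1 lists sleep disturbance, constipation, chest pain, shortness of breath, difficulty concentrating and depression among possible varenicline effects. Patients of a cancer-center lung/thoracic clinic (section 2.0) or a gynecologic surgery center (added in section 3.2) may plausibly have some of these before they take anything.

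Two errors follow, in opposite directions. A symptom present at entry can be recorded as a side effect, and a real worsening from an existing level can pass as background. Both matter because this checklist is the only structured safety instrument the protocol describes and it feeds the reporting decision. A mood complaint at Week 1 likewise has no earlier reading on the same items to set beside it. Participants also choose or decline either drug, so users of the two drugs may differ in symptoms at entry, and a descriptive table by drug would not reveal this.

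**Working it through.** **Schedule check.** The documents give no side-effect rate by arm, no power and no target for side effects, so there is no planned figure to reproduce. The check is whether any contact before treatment has a symptom reading.

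| Contact | Collected (section 3.3) | Symptom reading |
|---|---|---|
| Intake | Demographics, smoking history, beliefs about cessation aids, pregnancy screen, NMR blood | None |
| Week 0 call | Arm disclosed, medication offered | None |
| Week 1 call | Medication use, quit date or smoking rate, side effects | First |
| Week 4 visit | Same items, plus carbon monoxide if reporting cessation | Second |

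Both readings come after the offer, which agrees with the two time points in section 4.2.

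**Illustration of size.** Let b be the proportion with a given symptom before treatment and d the proportion of the others who develop it on treatment. If every existing symptom persists and is reported:

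- proportion reporting the symptom on treatment = b + (1 − b)d
- share of those reports that pre-date treatment = b / [b + (1 − b)d]

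The only documentary anchor is in section 4.1, which says that the common varenicline effects can occur in more than 5% of users; d = 5% is therefore the floor. All values of b, and d = 10% and 20%, are assumptions. For b = 20% and d = 10%: 0.20 + 0.80 × 0.10 = 0.28, and 0.20 / 0.28 = 71%.

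| Pre-existing share | b = 5% | b = 10% | b = 20% | b = 40% |
|---|---|---|---|---|
| d = 5% | 51% | 69% | 83% | 93% |
| d = 10% | 34% | 53% | 71% | 87% |
| d = 20% | 21% | 36% | 56% | 77% |

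The range is 21% to 93%. The lowest value is 0.05 / (0.05 + 0.95 × 0.20) = 0.05 / 0.24; the highest is 0.40 / (0.40 + 0.60 × 0.05) = 0.40 / 0.43. The grid concerns common effects, not the serious mood effects that section 4.1 puts at about 1 in 1000.

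**Can the randomised comparison stand in for a baseline?** Arms differ in the recommendation given, not in an assigned drug. Assume 50 per arm (about 100 at 1:1) and drug uptake of 70% versus 50%. The expected arm difference in a symptom is (1 − b) × d × 0.20. Over b = 5–40% and d = 5–20% this runs from 0.60 × 0.05 × 0.20 = 0.6 points to 0.95 × 0.20 × 0.20 = 3.8 points, with power of about 3–7%. The arm comparison does not recover the information.

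**What a baseline would not do.** Section 4.1 says withdrawal lasts 10–14 days. Week 1 is day 7 after the pre-quit call, so anyone who quit between that call and Week 1 is still inside the window. Week 4 is day 28. Withdrawal would be over for anyone who quit by day 28 − 14 = 14, or by day 28 − 10 = 18 at the shorter duration. The information that separates withdrawal from drug effect is therefore quit date and medication use, which both contacts already collect.

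**The case against.** The strongest reply is that nothing planned depends on this. Side effects are a monitoring item; the SAP analyses feasibility, acceptance, matching, abstinence and expectancies. That stands, and it limits the point to safety data and descriptive tolerability. A reader might take the background section's reference to minimising side effects as a hypothesis of this trial. It describes what earlier studies found; the premise stated for this trial concerns medication uptake and effectiveness.

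Second, the checklist is a screen. Under section 5.0 a designated individual decides the course of action on a potential adverse event, and key personnel including the study physician review data throughout. The physician also assesses contraindications at entry (section 2.0), and participants are under an attending physician's care when medication starts (section 4.2). So clinical information from before treatment exists. It is an eligibility judgement and a chart, however, not a recorded level on the same items.

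Third, the checklist's wording and the IRB procedure for adverse events are not in the documents. Section 3.3 says only: "In addition, the research assistant will ask about medication usage and side-effects". The form might ask about change since starting medication. For that reason symptoms *can* be recorded as side effects; the documents do not show that they *will* be.

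Fourth, a reader who sees that insomnia, constipation and difficulty concentrating appear both in the withdrawal list and among varenicline effects might infer that the missing baseline is why withdrawal and drug effects cannot be told apart. The documents do not support that. Withdrawal begins after quitting, so a reading before treatment would not separate the two, and quit date and medication use already help, particularly at Week 4.

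**Conclusion.** The point holds as a gap in the safety data. No symptom reading precedes the offer of medication, so the checklist cannot identify symptoms present at entry or show worsening from that level. The gap does not depend on recruitment from one clinic.

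The size is not known from the documents. The 21–93% range is an illustration that rests on assumed background (5–40%) and onset (5–20%, of which only the 5% floor comes from section 4.1), and on existing symptoms persisting and being reported. The shares fall if some existing symptoms resolve or are not reported. The range does show that pre-existing symptoms could be anything from a minority to nearly all of the reports, and the planned data could not show which.

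It does not follow that the trial's outcomes are biased, or that a baseline would resolve attribution to withdrawal. This is a cheap improvement worth making before enrolment, since a missed baseline cannot be reliably recovered later.

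**What to change.** Give the same checklist, including any mood items, once before treatment: either with the in-person intake survey or on the pre-quit call before medication is offered. Mark it in the measures table in section 3.3 and amend the count of time points in section 4.2.

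Keep recording every symptom at Weeks 1 and 4 and leave the adverse-event reporting rules unchanged. Add one field to each recorded symptom: pre-existing, new, or worse than the first reading. Tabulate these descriptively by medication actually taken (patch, varenicline, none) and by timing relative to quit date. The second split is needed because a new-or-worse flag alone would still include withdrawal symptoms.

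The cost is a few minutes of participant time at a contact that already takes place, with no new visit. A serious mood response found before treatment will need to be passed to the study physician, so staff should know this in advance. No SAP outcome or model changes.

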Approximately 100 adult current smokers (≥ 5 cigarettes/day), who are patients at the Helen F. Graham Cancer Center & Research Institute (Christiana Care) lung/thoracic clinic who are ages 18 and older. Exclusion criteria include: 1) use of non-cigarette tobacco products or current TUD treatment, 2) psychiatric or other medical contraindications to receiving TUD medication (assessed by the study physician), 3) no telephone, 4) medical instability, 7) inability to communicate in English, 8) unable to consent due to mental status, 9) estimated life expectancy of < 6 months, 10) pregnancy.

The duration of study participation will be approximately 6 weeks from the first through the final study visit.

3.0 STUDY PROCEDURES:

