3.2 Participant Identification and Recruitment

With the support of [name], thoracic surgeon, and lead for the "Lung Health Clinic" in the Helen F. Graham Cancer Center & Research Institute and [name], gynecologist and Director of the Division of Minimally Invasive Gynecologic Surgery at ChristianaCare, the research assistant will meet with prospective participants in the clinic or the Center for Advanced GYN & Minimally Invasive Surgery to screen for eligibility, discuss study

procedures, answer questions, and if appropriate review the consent and HIPPA forms. Patients will be clearly informed that not participating in this study will not preclude engaging in other smoking cessation programs, nor will accepting medication be a condition of participation.

Vulnerable Populations: Pregnant women and fetuses, children, neonates, and prisoners are not included in this research study. Women who are pregnant at the time of the baseline assessments will not be eligible for the study. Women will be advised to notify the study staff if they become or intend to become pregnant during the study period.

Populations vulnerable to undue influence or coercion: Educationally or economically disadvantaged persons are included but not solely targeted for recruitment. Cognitively impaired persons, including those with poorly managed serious psychiatric conditions, are not included in the current study.

The study consent includes language that informs participants that their care will not be affected if they choose not to participate in the study or withdraw after enrollment. The Principal Investigator may withdraw participants who violate the study plan, to protect the participant for reasons related to safety, or for administrative reasons. Whether or not each participant completes the study will be tracked.

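### Section 4.2 excludes women who intend to become pregnant, but Sections 2.0, 3.2 and 3.3 disqualify only current pregnancy, and no described step asks about intent at enrolment

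*Protocol*

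**What the plan says.** Four sections of the protocol state who is ineligible for reasons connected with pregnancy.

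- Section 4.2 (Protections Against Risks): "Pregnant women or women who intend to become pregnant will be excluded from participation". The sentence before it gives the practical measures: "female participants 55 and under will be screened for pregnancy and advised to use birth control".
- Section 2.0 (Study Population), at the end of the exclusion list: "9) estimated life expectancy of < 6 months, 10) pregnancy".
- Section 3.2 (Participant Identification and Recruitment): "Women who are pregnant at the time of the baseline assessments will not be eligible for the study". It then adds: "Women will be advised to notify the study staff if they become or intend to become pregnant during the study period".
- Section 3.3 (Study Procedures & Data Collection), intake session: "A pregnancy screen will be administered for women capable of becoming pregnant (55 and under"). The note attached to that step makes pregnant women ineligible and says nothing about intent.

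The SAP does not address the point. Its Aim 1 does, however, report the numbers and proportions of patients found eligible and enrolled.

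**The concern.** Section 4.1 warns that both study medications could seriously harm an unborn or breast-fed child. Section 4.2 answers that risk with several measures, one of which is the exclusion of women planning a pregnancy. A reader of the risk section, including an IRB member, would count that exclusion among the safeguards. A research assistant working from the Section 2.0 list and the Section 3.3 intake steps would find no instruction to apply it.

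Two things are at stake. The first is whether a stated protection reaches the women it is meant for. The second is whether eligibility is decided in the same way for everyone, which bears on the feasibility counts that Aim 1 exists to report.

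**Working it through.** The plan gives no figure on this point, so the check is mainly a comparison of texts.

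**Step 1. What each section does with pregnancy and with intent.**

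| Section | Current pregnancy | Intent to become pregnant |
|---|---|---|
| 2.0 exclusion list | Excluded | Not mentioned |
| 3.2 recruitment | Not eligible if pregnant at baseline | To be reported to staff; no consequence stated |
| 3.3 intake session | Screened; not eligible | Not mentioned |
| 4.2 protections | Excluded | Excluded |

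All four sections agree on current pregnancy. Only one of the four excludes intent.

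**Step 2. Whether any described procedure establishes intent at enrolment.** The intake survey in Section 3.3 covers personal characteristics, past smoking and attitudes to cessation aids. The schedule of measures lists demographics, smoking history, NMR, a combined item on medication, smoking and side effects, and carbon monoxide. None of these is described as asking about intent. The intake pregnancy screen is the natural place for such a question, but its content is not described, and the only disqualifying result given for it is pregnancy.

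**Step 3. Whether the notification sentences fill the gap.** Section 3.2 asks women to tell staff if they become pregnant or come to intend it. Section 4.2 asks them to tell staff only if they become pregnant. The two differ in scope, and neither says what staff do with the information.

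**Step 4. Timing.** The screen takes place at intake. Medication is offered at the pre-quit call, about 7 to 14 days later, and no repeat screen is described. The screen's only stated result therefore describes status before medication is offered, whereas intent concerns the weeks that follow.

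**Step 5. Size for Aim 1, per woman.** Take n = 100 enrolled (the approximate number in Section 2.0), of whom k meet some feasibility measure, such as accepting medication.

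- Leaving out one woman who did not meet the measure changes the proportion from k/100 to k/99. The difference is k/9900, and because k is at most 99 it cannot exceed 99/9900 = 0.01.
- Leaving out one woman who did meet it changes k/100 to (k − 1)/99. The difference is (100 − k)/9900, and because k is at least 1 it again cannot exceed 0.01.
- For the eligible or enrolled proportion among those approached, the denominator N is at least 100 if 100 enrol, so one woman moves it by 1/N, at most 0.01.

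Each woman classified differently therefore shifts a feasibility proportion by at most about 1 percentage point. The documents give neither the number of women aged 55 and under nor the share planning a pregnancy, so the total shift cannot be calculated.

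**Step 6. Aim 2.** Eligibility is settled at intake, before randomization, so an inconsistent rule on intent applies to both arms alike and gives no reason to expect bias in the comparison between them.

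**The case against.** The strongest reply is that Section 4.2 is itself part of the protocol and excludes these women in plain terms. On that view it adds to Section 2.0. The Section 2.0 list is not presented as exhaustive, its numbering skips from 4 to 7, and no section says that a woman planning pregnancy is eligible. Incomplete repetition of a criterion would then be a better description than contradiction.

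Part of this stands. A reader might infer that the safeguard does not operate at all, or that a woman who reports intent can never be removed. The documents do not support either reading. Section 4.2 excludes her, and Section 3.2 lets the investigator withdraw a participant "to protect the participant for reasons related to safety, or for administrative reasons". That power is discretionary, applies after enrolment and is not tied to intent, so it is a possible route and not the exclusion that Section 4.2 promises.

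A reader might also infer that the intake screen cannot detect intent. The text does not say whether the screen is a laboratory test, a set of questions or both. The consent pages were not available for review and the screening form is not among the documents, so intent may be raised there. The supportable statement is that no procedure for establishing intent is described.

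The Section 2.0 criterion on "psychiatric or other medical contraindications to receiving TUD medication (assessed by the study physician") does not close the gap. It does not mention intent, and the list gives pregnancy its own separate item.

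It is also fair to say that medication is optional and that other protections remain: the pregnancy screen, advice on birth control and notification of pregnancy. These limit the consequence. They do not remove the mismatch, because Section 4.2 excludes these women from participation and not merely from medication.

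**Conclusion.** The point holds as an inconsistency in the eligibility text with a safety consequence. Section 4.2 states an exclusion for intent that the other three sections do not carry and that no described criterion, intake step or scheduled measure applies. Staff following different sections could reach different decisions on the same woman.

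The statistical effect is small: at most about 1 percentage point per woman on an Aim 1 proportion, assuming about 100 enrolled, and no material effect on any Aim 2 estimate. Recruitment partly through a gynecologic surgery center might tempt a reader to put a number on the women affected, but any such number would rest on assumptions with no anchor in the documents. The case for correction rests on the risk section and the eligibility text describing different protections. The conclusion assumes only that the sections available are the ones staff work from; a consent form that raised intent would still leave them unreconciled.

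**What to change.** Reconcile Sections 2.0, 3.2, 3.3 and 4.2 so that all four carry one rule on intent to become pregnant. The investigator and the IRB decide which rule applies.

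- If the Section 4.2 exclusion is kept: list it in Section 2.0, add a question on intent to the intake screen in Section 3.3 (or state that the screen already asks), and align the Section 3.2 notification sentence with it, including what follows when intent is reported.
- If it is not kept: remove it from Section 4.2, so that the risk section does not claim a protection that the eligibility text does not apply.

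In either case, check that the consent form agrees with the rule chosen, and make the notification sentences in Sections 3.2 and 4.2 the same.

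The cost is a wording amendment, at most one question at a screen already planned, and, if the exclusion is kept, possibly some otherwise eligible women not enrolled. The SAP needs no change.
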